#### 7.3.1 Reporting Pregnancy

##### 7.3.1.1 Maternal exposure

If a patient becomes pregnant during the course of the study, the study treatment should be discontinued immediately and the pregnancy reported to the Sponsor. The potential risk of

exposure of the fetus to the investigational agent(s) or chemotherapy agents (s) should be documented in box B5 of the MedWatch form “Describe Event or Problem”.

Pregnancy itself is not regarded as an AE unless there is a suspicion that the study treatment under study may have interfered with the effectiveness of a contraceptive medication. However, as patients who become pregnant on study risk intrauterine exposure of the fetus to agents which may be teratogenic, the CCR is requesting that pregnancy should be reported in an expedited manner as **Grade 3 “Pregnancy, puerperium and perinatal conditions - Other (pregnancy)”** under the **Pregnancy, puerperium and perinatal conditions** SOC.

Congenital abnormalities or birth defects and spontaneous miscarriages should be reported and handled as SAEs. Elective abortions without complications should not be handled as AEs. The outcome of all pregnancies (spontaneous miscarriage, elective termination, ectopic pregnancy, normal birth, or congenital abnormality) should be followed up and documented.

If any pregnancy occurs in the course of the study, then the investigator should inform the Sponsor within 1 day, i.e., immediately, but **no later than 24 hours** of when he or she becomes aware of it.

The designated Sponsor representative will work with the investigator to ensure that all relevant information is provided to the Sponsor within 1 to 5 calendar days for SAEs and within 30 days for all other pregnancies.

The same timelines apply when outcome information is available.

#### 7.3.1.2 Paternal exposure

Male patients should refrain from fathering a child or donating sperm during the study and for 4 months after the last dose of rhIL-15.

Pregnancy of the patient’s partner is not considered to be an AE. However, the outcome of all pregnancies (spontaneous miscarriage, elective termination, ectopic pregnancy, normal birth, or congenital abnormality) occurring from the date of the first dose until 4 months after the last dose should, if possible, be followed up and documented.

### 7.4 DATA AND SAFETY MONITORING PLAN

#### 7.4.1 Principal Investigator/Research Team

The clinical research team will meet on a weekly basis when patients are being actively treated on the trial to discuss each patient. Decisions about dose level enrollment and dose escalation if applicable will be made based on the toxicity data from prior patients.

All data will be collected in a timely manner and reviewed by the principal investigator. Adverse events will be reported as required above. Any safety concerns, new information that might affect either the ethical and or scientific conduct of the trial, or protocol deviations will be immediately reported to the IRB using iRIS and if applicable to the Sponsor.

The principal investigator will review adverse event and response data on each patient to ensure safety and data accuracy. The principal investigator will personally conduct or supervise the investigation and provide appropriate delegation of responsibilities to other members of the research staff.

#### 7.4.2 Sponsor Monitoring Plan

As a sponsor for clinical trials, FDA regulations require the CCR to maintain a monitoring program. The CCR's program allows for confirmation of: study data, specifically data that could affect the interpretation of primary study endpoints; adherence to the protocol, regulations, and SOPs; and human subjects protection. This is done through independent verification of study data with source documentation focusing on:

- Informed consent process
- Eligibility confirmation
- Drug administration and accountability
- Adverse events monitoring
- Response assessment.

The monitoring program also extends to multi-site research when the CCR is the coordinating center.

This trial will be monitored by personnel employed by a CCR contractor. Monitors are qualified by training and experience to monitor the progress of clinical trials. Personnel monitoring this study will not be affiliated in any way with the trial conduct.

## **8 STATISTICAL CONSIDERATIONS**

The primary objective of this trial is to determine the safety, toxicity profile, DLT and MTD of CIV rhIL-15 administered for 10 consecutive days (240 hours) or 5 consecutive days (120 hours) in subjects with metastatic unresectable cancers for which curative or palliative measures either do not exist or are not associated with a survival advantage.

The secondary objectives include determination of rhIL-15 PK, including time to reach serum steady state, decline if any at later time points, changes in serum concentration associated with the expected lymphocytosis and decline following discontinuation of the CIV infusion; characterization of the biological effects of rhIL-15 on the percentages and absolute numbers of circulating lymphocyte sets (NK and T-cells) and T-cell subsets (naïve, central or effector memory subsets based on expression of CD56, CD4, CD8, CD45RO, CD45RA, CD28, CD95, CCR7 and CD62L) by flow cytometry and the plasma levels of pro-inflammatory cytokines. The potential antitumor activity of rhIL-15 will be assessed by the clinical response rate and time to progression in this patient population; and assessment of the nature of T-cell infiltration and cytokine and check-point inhibitor gene expression by analysis of pre- and post-treatment biopsies obtained from selected patients with easily accessible tumor deposits. All evaluations of these secondary endpoints will be considered exploratory.

There are 9 planned dose levels for this trial that will enroll 3 to 6 patients each using a modified Fibonacci design to define the MTD for CIV rhIL-15.

The MTD for each schedule will be based on the assessment of DLT during the first cycle of treatment, and will be defined as the dose level at which less than one-third of patients (0/3 or 0-1/6 patients) treated at that dose experience a DLT, with the next higher dose level demonstrating a one-third or greater number of patients ( $\geq 2/3$  or  $\geq 2/6$  patients) having DLT. If a patient did not experience DLT and did not finish 1 cycle of treatment (either 42 or 21 days), he or she will not be evaluable for determination of the MTD and will be replaced in the dose level. An additional 3 to 6 patients will be enrolled at the MTD or, if no severe or dose-limiting toxicities are encountered, the maximum administered dose of rhIL-15, so that a total of 9 patients will potentially be treated at MTD for either schedule to better characterize the clinical activity of

CIV rhIL-15 in this patient population. If feasible, the patients enrolled in this expansion cohort will be limited to histologic cancer subtypes previously shown to be sensitive to immunotherapy (renal cell carcinoma, melanoma, prostate, colorectal and ovarian cancer).

As of April 2016, twenty-four evaluable patients have enrolled on Dose Levels 1-6; with 2 more to be enrolled in Dose Level 6 after Amendment G. A maximum of 6 evaluable patients may be enrolled at DL 7 & 8 with an additional 9 at DL 9. If all dose levels are evaluated (with 6 patients per remaining dose levels and 9 total patients at the MTD or maximum administered dose), a maximum of 47 evaluable patients will be enrolled. An additional 5 patients may be enrolled to compensate for inevaluable patients; thus, bringing the maximum accrual ceiling to 52.

Similarly, if all dose levels are evaluated, the minimum number of patients required will be 41 (24 evaluable patients have enrolled at DL 1-6; with 2 more to be enrolled in Dose Level 6 after Amendment G and with 3 patients enrolled at DL 7 & 8; 9 at DL 9; and 5 inevaluable patients a minimum of 46 will be reached).

Patients with tumors known to have tumor markers (PSA, CEA, CA125) will have the serum level of these markers assessed at the time of their radiographic restaging to gain further insight into the potential efficacy of rhIL-15 treatment. If tumor markers are initially above the upper limit of normal, they must normalize for the patient to be considered a complete response. Specific guidelines for serum tumor markers previously reported (CA125 and PSA) will be used to assess responses to rhIL-15 treatment.

Using the two dose escalation schedules, the probability of escalating to the next dose level, based on the true rate of DLT at the current dose for each schedule, is given by the following table (each group will be considered independently of the other):

True Toxicity at a Given Dose	10%	20%	30%	40%	50%	60%
Probability of Escalating	.91	.71	.49	.31	.17	.08

Thus, if the true underlying proportion of DLTs is 50% at the current dose, there is a 17% chance of escalating to the next dose.

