### **3.3 DOSE ESCALATION**

Dose escalation will proceed in cohorts of 3 to 6 patients. Patients will not begin treatment at the next higher dose level until all patients treated at the previous dose level have reached day 21 of the protocol, recovered from any clinical or laboratory toxicities and would be able to initiate another cycle of treatment unless restaging has demonstrated progression of their disease). The MTD is the dose level at which no more than 1 of up to 6 patients experience DLT, and the dose below that at which at least 2 (of  $\leq$  6) patients have DLT as a result of the drug. If a patient did not experience DLT and did not finish 1 cycle of treatment (42 days), he or she will not be evaluable for determination of the MTD and will be replaced in the dose level.

Dose escalation will follow the rules outlined in the Table below.

Number of Patients with DLT at a Given Dose Level	Escalation Decision Rule
0 out of 3	Enter up to 3 patients at the next dose level
$\geq 2$	Dose escalation will be stopped. This dose level will be declared the maximally administered dose (highest dose administered). Up to 3 additional patients will be entered at the next lowest dose level if only 3 patients were treated previously at that dose.
1 out of 3	Enter up to 3 more patients at this dose level. 

• If 0 of these 3 patients experience DLT, proceed to the next dose level.

• If 1 or more of this group suffer DLT, then dose escalation is stopped, and this dose is declared the maximally administered dose. Up to 3 additional patients will be entered at the next lowest dose level if only 3 patients were treated previously at that dose.

$\leq 1$ out of 6 at highest dose level below the maximally administered dose	This is the MTD and is generally the recommended phase 2 dose. At least 6 patients must be entered at the recommended phase 2 dose.

The MTD has already been defined for patients treated with the 10-day regimen. For patients treated with the 5-day regimen dose escalation will continue through the 5 mcg/kg/day dose level in the absence of  $\geq 2$  DLTs for the patients treated for any of the dose levels being evaluated for the 5-day regimen. If an MTD is not identified up to 9 patients may be treated at the maximum administered dose (MAD) of 5 mcg/kg/day to better evaluate the therapeutic potential of rhIL-15 given by this schedule.

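### For the 5-day schedule, Sections 3.3 and 8 disagree on whether an MTD may rest on three patients and on the evaluability window, and the minimum of 41 patients counts an expansion that the Schema makes conditional

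*Combined protocol and SAP*

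**What the plan says.** Only the 5-day cohorts (Dose Levels 7 to 9) are affected. Section 3.3 says of the other schedule: "The MTD has already been defined for patients treated with the 10-day regimen". The Schema records that the 5-day MTD is still open.

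**Number of patients behind the MTD.** Section 8 sets the criterion for each schedule: "less than one-third of patients (0/3 or 0-1/6 patients) treated at that dose experience a DLT", with the next higher dose showing DLT in one third or more. The prose of Section 3.3 reads: "The MTD is the dose level at which no more than 1 of up to 6 patients experience DLT". The table in Section 3.3 is stricter. Its last row identifies the MTD by at most 1 DLT in 6 and adds: "At least 6 patients must be entered at the recommended phase 2 dose". When a dose fails, the table directs: "Up to 3 additional patients will be entered at the next lowest dose level if only 3 patients were treated previously at that dose".

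**Evaluability.** In Section 3.3 a DLT-free patient is replaced if he or she "did not finish 1 cycle of treatment (42 days"). The matching sentence in Section 8 reads "did not finish 1 cycle of treatment (either 42 or 21 days"). Sections 3.1 and 3.8.2 fix all 5-day cycles at 21 days, and DLT is judged in the first cycle (Sections 3.2.1 and 8).

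**Accrual.** Section 8 gives a minimum of 41 evaluable patients (46 with five inevaluable) and a maximum of 47 (52), counting nine at Dose Level 9 in both. Section 3.1 repeats 41 to 47 in total and 17 to 23 still to enrol. Section 8 says that "a total of 9 patients will potentially be treated at MTD for either schedule". The Schema grants the 5-day schedule nine patients only if at least one 5-day patient has a confirmed partial or complete response, and otherwise rules out any 5-day expansion. Section 3.3 permits up to nine at the maximum administered dose and names no response condition.

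**The concern.** The MTD is a primary objective, and on the 5-day schedule it has yet to be declared. A reader who applies the Section 8 definition can name an MTD on three patients; a reader who applies the Section 3.3 table cannot. The same two sections give different windows for deciding which DLT-free patients stay in the DLT denominator. The expansion to nine does not remove the first problem: Section 8 describes it only as potential, and the Schema withholds it on this schedule unless a response is confirmed. That same condition undercuts the stated minimum sample size.

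**Working it through.** **1. The plan's own figures reproduce.** With true DLT rate p, the chance of escalating (0/3, or 1/3 followed by 0/3) is (1−p)³ + 3p(1−p)⁵. For p = 10% to 60% this gives .906, .709, .494, .309, .172 and .082, matching the Section 8 table (.91, .71, .49, .31, .17, .08). The accrual sums also reproduce: 24+2+3+3+9 = 41 and 24+2+6+6+9 = 47; adding five gives 46 and 52. Still to enrol: 2+3+3+9 = 17 and 2+6+6+9 = 23.

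**2. Three patients or six.** One-sided 95% exact upper limits for the DLT rate:
- 0/3: 1 − .05^(1/3) = 63%
- 0/6: 1 − .05^(1/6) = 39%
- 1/6: 58%

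Now suppose the next dose fails. Under Section 8, a dose qualifies as the MTD with the escalation probability above. Under the Section 3.3 table it needs at most 1 DLT in 6: (1−p)⁶ + 6p(1−p)⁵. The difference is the chance of 0/3 followed by at least 2 DLTs in three more patients: (1−p)³ × [3p²(1−p) + p³].

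| True DLT rate | ≥2 of next 3, given 0/3 | 0/3 then ≥2/3 (joint) | Qualifies, Section 8 | Qualifies, 3.3 table |
|---|---|---|---|---|
| 10% | .028 | .020 | .91 | .89 |
| 20% | .104 | .053 | .71 | .66 |
| 30% | .216 | .074 | .49 | .42 |
| 40% | .352 | .076 | .31 | .23 |
| 50% | .500 | .063 | .17 | .11 |

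**3. Evaluability window.** Forty-two days is two 21-day cycles. A DLT-free 5-day patient who leaves on days 22 to 41 is replaced under the literal figure in Section 3.3 and counted under Section 8. Such departures are plausible: first restaging falls on days 14 to 21 of cycle 2 (Section 3.8.2, note 7), about study days 35 to 42, and progression ends treatment (Section 3.10.1). Section 3.3 also lets the next dose open once patients reach day 21 and have recovered. Read literally, a patient who supported escalation could later become inevaluable.

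**4. Minimum accrual.** Take all three 5-day levels evaluated, 0/3 at each, and no confirmed response:
- three at the top level: 24+2+3+3+3 = 35 (40 with five inevaluable; 11 still to enrol)
- six at the top level, if the Section 3.3 requirement for the recommended phase 2 dose is applied there: 24+2+3+3+6 = 38 (43; 14 still to enrol)

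The stated 41 is therefore 6 or 3 too high as a minimum.

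**The case against.** The best reply is that the sections can be read together: Section 3.3 gives the procedure and Section 8 only the rate threshold. If the table is followed, a three-patient level below a failing dose is back-filled, and 2/6 would then fail the Section 8 threshold too. A three-patient MTD arises only if the back-fill is skipped or cut short. This is right about the likely intent, and it means the probabilities above apply only when the back-fill is not done. It does not make the text consistent. Section 8 accepts 0/3 outright, neither prose definition mentions the back-fill, and the back-fill itself is worded as a ceiling of three. Section 8 also adds 3 to 6 patients to reach nine, which fits an MTD resting on three (3+6 = 9).

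On the window, the 42 days looks like text left from the 10-day schedule, and the reference to one cycle points to 21 days. That is the more natural reading, so this is the weaker part. Still, 42 is the only figure given in the section that governs escalation.

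On accrual, 41 is correct arithmetic, drives no dose decision, and leaves the maximum of 47 and the ceiling of 52 untouched. All true; but it is stated as a required minimum and counts patients the Schema may not allow.

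**Conclusion.** The concern holds on all three parts. The MTD threshold and the minimum accrual are the strongest; the window is most likely a leftover. The effect on the declared 5-day dose is modest: 2 to 8 percentage points in the chance that a dose qualifies, for true DLT rates of 10% to 50%. Those figures are conditional on the next dose failing and on the back-fill being omitted, so the unconditional effect is smaller. The minimum of 41 should be 35 or 38 when all levels are evaluated, each shows 0/3 and no response is confirmed; stopping escalation early could give fewer. The inconsistencies should be corrected because they touch the decision rule for a primary objective and a stated sample size. The escalation rule and its probability table are sound as written.

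**What to change.** 1. Make one minimum number apply to the MTD in the Section 8 definition, the Section 3.3 prose and the Section 3.3 table. One way is to drop the 0/3 alternative from Section 8 and align the 3.3 prose with the table's six. State that the back-fill is separate from the response-dependent expansion in the Schema.
2. Make the day count in the Section 3.3 evaluability sentence schedule-specific, as Section 8 already does.
3. Reconcile the Schema, Section 3.3 and Section 8 on how many patients are treated at the maximum administered dose when no response is confirmed. Then restate the minimum in Section 8 (41 and 46) and the ranges in Section 3.1 (41 to 47; 17 to 23).

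The cost is protocol wording. No patients are added beyond the up to three that the Section 3.3 table already back-fills, and the maximum of 47 evaluable patients and the escalation probabilities stay the same.

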## SCHEMA

Patient Cohort	Number of Patients	Dose of CIV rhIL-15 (mcg/kg/day x 10 days)*
1	3 to 6	0.1
2	3 to 6	0.25
3	3 to 6	0.5
4	3 to 6	1
5	3 to 6	2
6	3 to 6	4
		Dose of CIV rhIL-15 (mcg/kg/day x 5 days)**
7	3 to 6	3
8	3 to 6	4
9	3 to 6	5

\*Nine total patients will be treated at the MTD. The MTD for the 10-day dosing schedule has been identified as 2 mcg/kg/day.

The MTD has not yet been identified for the 5-day dosing schedule.

\*\* If there is a confirmed response (partial or complete response) in at least one patient in the 5-day dosing cohorts, a total of nine patients will be treated at the MTD or the maximum administered dose. Otherwise, there will not be an expansion cohort for any dose in the 5-day dosing cohorts.

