### **3 STUDY IMPLEMENTATION**

#### **3.1 STUDY DESIGN**

This is a Phase I open-label, non-randomized, dose-escalation safety trial of CIV rhIL-15 that will enroll 41 to 47 evaluable patients with metastatic unresectable cancers for which curative or palliative measures either do not exist or are not associated with a survival advantage.

Patients will receive CIV rhIL-15 for 10 consecutive days (240 hours) and will be assigned to a dose level sequentially based on their order of entry into the study. The starting dose will be 0.1 mcg/kg/day and in the absence of significant toxicities, dose escalation will proceed to evaluate dose levels of 0.25, 0.5, 1, 2 and 4 mcg/kg/day. Cycles 1 and 2 will be 42 days in length, but all subsequent treatment cycles will be 28 days in length with an additional 7 days on either schedule allowed for reasons other than recovery for treatment-related toxicities. Subjects will have to demonstrate an absence of anti-IL-15 antibodies in their post-treatment (day 12 and week 4) assessments before additional cycles of rhIL-15 can be initiated.

Radiologic reassessments for 10-day treatment cycle patients will be performed during week 4 (days 26 to 35) of Cycles 1 and 2 and at off-treatment and off-study visits.

After treatment of patients in the expansion cohort for the 10-day schedule is completed, new cohorts of 3 to 6 patients each will begin treatment with the 5-day (120 hour) schedule at dose levels of 3, 4 or 5 mcg/kg/day to define the MTD for this shorter CIV rhIL-15 regimen. All treatment cycles for these cohorts will be 21 days in length.

As of April 2016, twenty-four evaluable patients have enrolled on Dose Levels 1-6; with 2 more to be enrolled in Dose Level 6 after Amendment G. When the study is re-opened for enrollment, an additional 17-23 evaluable patients will be enrolled.

A total of 9 patients will potentially be treated at the MTD or maximum administered dose for both schedules to better characterize the clinical activity of CIV rhIL-15 in this patient population.

Radiologic reassessments for both the 10day and 5-day dosing cohorts will be performed after every other cycle (2, 4, 6, 8 etc.) including the subjects that go onto to receive additional cycles of treatment.

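### The stated minimum of 41 evaluable patients counts a 5-day expansion to nine that the schema allows only after a confirmed response

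*Combined protocol and SAP*

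**What the plan says.** Section 8 plans the cohorts as follows: "There are 9 planned dose levels for this trial that will enroll 3 to 6 patients each". It gives a maximum of 47 evaluable patients and an accrual ceiling of 52, and then says that "if all dose levels are evaluated, the minimum number of patients required will be 41". The parenthesis that follows shows the make-up: 24 already enrolled at DL 1-6, two more for DL 6, three each at DL 7 and DL 8, and nine at DL 9. Adding five inevaluable patients gives 46. Section 3.1 says the trial "will enroll 41 to 47 evaluable patients" and puts further accrual after re-opening at 17 to 23.

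The schema footnote for the 5-day schedule sets a condition on the nine: "If there is a confirmed response (partial or complete response) in at least one patient in the 5-day dosing cohorts", nine in total are treated at the MTD or maximum administered dose. It continues: "Otherwise, there will not be an expansion cohort for any dose in the 5-day dosing cohorts".

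The other sections describe the expansion without that condition:
- Section 8: "An additional 3 to 6 patients will be enrolled at the MTD", or at the maximum administered dose if no severe or dose-limiting toxicity is met, "so that a total of 9 patients will potentially be treated at MTD for either schedule". It then calls these added patients an expansion cohort.
- Section 3.1 also describes nine as a possibility, for both schedules.
- Section 3.3 says up to nine may be treated at the maximum administered dose if no MTD is found.

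On the number needed at the selected dose, section 8 defines the MTD as the level where "less than one-third of patients (0/3 or 0-1/6 patients) treated at that dose experience a DLT" and the next level up shows too many DLTs. The section 3.3 table requires at least six patients at the recommended phase 2 dose.

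**The concern.** A figure labelled as the minimum required has to hold in the smallest branch that the plan permits. If no 5-day patient has a confirmed response, the schema forbids the nine patients that section 8 counts.

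Someone working from section 3.1, 3.3 or 8 alone cannot see that the 5-day expansion depends on response. That person could plan or report accrual against a lower bound that the schema does not support, or could start an expansion that the schema rules out.

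**Working it through.** This is a count by dose level; no power formula applies.

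**Inputs.** From section 8: 24 evaluable at DL 1-6, 2 more at DL 6, 3 to 6 per level, 9 at DL 9, and 5 inevaluable. From the schema: nine on the 5-day schedule only after a confirmed response. From section 3.3: at least six at the recommended phase 2 dose.

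**The plan's own figures.**
- Minimum: 24 + 2 + 3 + 3 + 9 = 41. Further: 2 + 3 + 3 + 9 = 17. With inevaluable: 41 + 5 = 46.
- Maximum: 24 + 2 + 6 + 6 + 9 = 47. Further: 2 + 6 + 6 + 9 = 23. Ceiling: 47 + 5 = 52.

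All agree with the text.

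**No confirmed response, all levels evaluated, at least three per level.**
- Three suffice at the selected dose: 24 + 2 + 3 + 3 + 3 = 35. Further: 2 + 3 + 3 + 3 = 11. With inevaluable: 40.
- At least six at the selected dose, DL 9 selected: 24 + 2 + 3 + 3 + 6 = 38. Further: 2 + 3 + 3 + 6 = 14. With inevaluable: 43.
- At least six, escalation stopped at DL 9 after three patients and DL 8 filled to six: 24 + 2 + 3 + 6 + 3 = 38, again 14 further and 43 with inevaluable.
- Maximum in this branch: 24 + 2 + 6 + 6 + 6 = 44.

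**Difference from 41.** 41 - 38 = 3 and 41 - 35 = 6, which is 3/41 = 7.3% to 6/41 = 14.6%. Against the 17 further patients it is 3/17 = 17.6% to 6/17 = 35.3%.

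**Why there are two values.** Section 8 accepts 0 of 3 at the MTD, while section 3.3 asks for at least six at the recommended phase 2 dose. Section 8 also calls the additional 3 to 6 patients at the MTD the expansion cohort. If three were treated first, patients four to six fall under that label, and the schema would bar them without a response while section 3.3 would require them. If they belong to the planned cohort of 3 to 6, there is no clash and 38 is reachable.

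**Is the no-response branch realistic?** The documents give no expected response rate. Assuming a true confirmed-response rate p, the chance of no response in nine patients (three at each 5-day level) is (1 - p)^9:

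| p | Chance of no response in nine |
|---|---|
| 2% | 83% |
| 5% | 63% |
| 10% | 39% |
| 20% | 13% |

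Section 1.2.1.4 reports no clinical responses among 18 subjects in the IV bolus trial. Schedule and population differ, so that is background only.

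**The case against.** The strongest reply is that 41 is an openly disclosed scenario. Its parenthesis lists nine at DL 9, and the paragraph follows a maximum built on the same nine, so it can be read as the lower end of accrual given expansion. Sections 3.1, 3.3 and 8 all use conditional verbs about the nine, and the schema at the front of the same document gives the trigger.

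Most of this is right, and it limits the point. The sum is correct, and a reader is told that nine is not certain. But the conditional wording also confirms that nine is not required, so it cannot form part of a required minimum. The scenario reading needs an assumption of expansion that the sentence does not state.

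It is also fair to say that the documents do not fix a replacement. Both 35 and 38 rest on stated assumptions, and the choice between them depends on a conflict between sections 8 and 3.3.

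A reader might go further and infer that the sample size is miscalculated, that the trial will over-enrol, or that the dose-finding properties are compromised. The documents do not support this. The stated sums reproduce, 41 is right if a response is confirmed, the overall maximum and ceiling do not depend on it, and the escalation probabilities in section 8 follow from the DLT rule alone.

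**Conclusion.** The point holds and is minor. The figures 41, 46, 41 to 47 and 17 to 23 take the 5-day expansion as given, while the schema makes it conditional and the other sections do not mention the condition.

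In the no-response branch the lower bound is overstated by 3 to 6 evaluable patients. This assumes, as section 8 does, that all dose levels are evaluated, with at least three patients at each; stopping at DL 7 or DL 8 would give fewer. Confidence is high in the mismatch. Neither 35 nor 38 can be called the correct minimum until the number required at the selected dose is settled.

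The 47 and 52 remain valid as bounds across both branches. It would be wrong to infer that 47 is reachable without a response, since the evaluable maximum there is 44. Only the stated lower bound of accrual and the consistency of the expansion rule are affected.

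**What to change.** Reconcile the expansion rule across the schema and sections 3.1, 3.3 and 8, and state it in the same terms in each. Which rule stands is for the sponsor.

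- **If the response condition is kept:** restate every linked figure together. The evaluable range becomes 35-47 (11-23 further), with 40 in place of 46, if three suffice at the selected dose. It becomes 38-47 (14-23 further), with 43 in place of 46, if at least six are required. State alongside that all levels are evaluated with at least three patients each.
- **If the condition is not kept:** remove it from the schema, make the nine definite in the other sections, and leave 41, 46, 41-47 and 17-23 as they are.

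If the condition is kept, also reconcile the number required at the selected dose between section 8 and the section 3.3 table. Say whether patients four to six there belong to the planned cohort of 3 to 6 or to the expansion.

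The cost is aligned wording in four places and, under the first option, a few restated numbers in sections 3.1 and 8. No patients are added beyond the existing maximum of 47 evaluable and ceiling of 52.
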